**Protocol Approved By:**

PRINCIPAL INVESTIGATOR:

CLINICAL LEAD CO-INVESTIGATOR

---

[name]

---

[name], MSN

---

Date

---

Date

EXECUTIVE SPONSOR:

---

[name], MBA

---

Date

PROTOCOL SUMMARY	
Study Title	Effect of Personalized Care Management on Hospital Inpatient Stays among High Utilizers: A Randomized Clinical Trial
Study Design	Parallel group randomized controlled trial evaluating inpatient encounters
Study Objectives	
The Multiple Visit Patient (MVP) program was rolled out to the first cohort of 600 patients in January 2019, and 46 additional patients were added in August 2019. Pre-post descriptive results show that the 2019 MVP cohort had 50% lower inpatient hospital admissions in 2019 than in 2018. While this is a promising outcome, without a randomized controlled trial (RCT) causal inferences cannot be made about the effect of the MVP program. Regression to the mean is a competing potential reason for observing the rate decrease, with high utilizers having lower hospital use over time even in the absence of any interventions. Thus, the Population Health leadership seeks to conduct a definitive trial to rigorously evaluate the MVP program effectiveness.
 
Primary Objective: To evaluate the effectiveness of enrollment in the MVP care management program compared to usual care on reducing 12-month total inpatient hospital utilization among patients with high past volume of hospital inpatient stays.
 
The Secondary Objectives are to
 
(1) evaluate the effect(s) of participation in the MVP program on:
 

• 6-month inpatient hospital utilization

• 6-month and 12-month Combined IP and OBS hospital stays at Atrium Health facilities

• 6-month and 12-month Combined IP and OBS hospital stays at AH and other facilities

• 6-month and 12-month IP hospital stays that are readmission eligible (using CMS criteria)

• 6-month and 12-month Readmissions

• 6-month and 12-month ED visits

• 6-month and 12-month Mortality

• 6-month and 12-month Hospital bed days (length of stay, IP)

• 6-month and 12-month Hospital charges

 
(2) assess variability in MVP program treatment effects associated with predefined patient and program factors, including:
 

▪ insurance status

▪ age, gender, race and ethnicity

▪ English as second language

▪ type of program (e.g., ACM, etc.)

▪ community characteristics

▪ clinical characteristics (e.g., CCI)

	
The exploratory analysis aims are to evaluate the effect of participation in the MVP program features on
 
 
• 6-month and 12-month primary care visits scheduled and attended / no show to a scheduled appointment
 
• 6-month and 12-month Healthy Days at Home
 
• 6-month and 12-month paid amount for the Medicare patient subgroup
 

Inclusion / Exclusion Criteria	
Inclusion criteria:
 
 
• Adults (18 years old or older)
 
• Patients with 4 or more inpatient hospital visits across Atrium Health Metro hospitals in 2019
 
 
Exclusion criteria:
 
 
• Existing MVP participants (enrolled in the 2019 MVP program cohort)
 
• Patients who at the time of identification for the MVP program are 
 
○ enrolled in a Levine Cancer Institute navigator program
 
○ enrolled in hospice or palliative care
 
○ attributed to a primary care provider at another healthcare system (e.g., Novant)
 
 
 
• Patients whose primary residence is a skilled nursing facility
 

Study Procedures	
The list of patients with four or more inpatient hospital visits in 2019 will be pulled from the Atrium Health electronic data warehouse (EDW) by IAS Clinical Quality Analytics, and eligibility for the MVP program of patients on this list will be determined by the Population Health's Care Management team based on predefined eligibility criteria. IAS CORE will randomize eligible participants into one of two groups: 1) MVP program; or 2) usual care.
 
Population Health's Multiple Visit Patient (MVP) care management program aims to manage health and lower hospital utilization among patients with a history of high inpatient hospital stays at Atrium Health. Patients eligible for the program have four or more inpatient visits over the 12-month period prior to enrollment. Once enrolled, each MVP program participant receives on-going support from an assigned MVP care manager and larger care management team, including the following core program components:
 
 
(1) customized care plan developed for each patient at the time of enrollment
 
(2) routine, virtual health monitoring and collaborative care management team-based review
 
(3) personalized navigation and coordination across multidisciplinary Atrium Health services, as needed
 
(4) education, health coaching, and support via telephonic and in-person interactions, as needed
 
 
The control group will receive usual care.

	Upon completion of the 12-month period during which outcomes data will be accrued, the study will evaluate whether 12-month participation in the MVP program care management program, compared to usual care, reduced inpatient hospital use.
Statistical Analysis	Analyses will include all patients meeting the inclusion and exclusion criteria. The effect of the MVP program (intervention) on primary and secondary outcomes will be estimated using multivariable regression analysis, including generalized linear models and Poisson regression models. Results will be presented as marginal effects and odds ratios where applicable, with 95% confidence intervals.

#### LIST OF ABBREVIATIONS

ACM	Ambulatory Care Management
AH	Atrium Health
AIM	Advanced Illness Management
CCNC	Community Care of NC
CCB	Community Care Bridge
CCP	Community Care Partners
CORE	Center for Outcomes Research and Evaluation
ED	Emergency Department
EDW	Enterprise Data Warehouse
HNHC	High-need high-cost
IP	Inpatient
MVP	Multiple Visit Patient
NC	North Carolina
OBS	Observation
SOP	Standard Operating Procedures

## 1. OBJECTIVES

### 1.1. Hypothesis

The MVP care management program, compared to usual care, leads to a decrease in inpatient hospital stays among patients with a historical high volume of hospital inpatient stays.

### 1.2. Primary Objective

Primary Objective: To evaluate the effectiveness of enrollment in the MVP care management program compared to usual care on reducing 12-month total inpatient hospital utilization among patients with a historical high volume of hospital inpatient stays.

### 1.3. Secondary Objectives

The Secondary Objectives are to

(1) evaluate the effect(s) of participation in the MVP program on:

- 6-month inpatient hospital utilization
- 6-month and 12-month Combined IP and OBS hospital stays at Atrium Health facilities
- 6-month and 12-month Combined IP and OBS hospital stays at AH and other facilities
- 6-month and 12-month IP hospital stays that are readmission eligible (using CMS criteria)
- 6-month and 12-month 30-day readmission rate among patients who had at least one encounter during the time frame
- 6-month and 12-month ED visit rate
- 6-month and 12-month Mortality rate
- 6-month and 12-month Hospital bed days (length of stay, IP)
- 6-month and 12-month Hospital charges

(2) assess variability in MVP program treatment effects associated with predefined patient and program factors, including:

- insurance status
- age, gender, race and ethnicity
- English as second language
- type of care management program (e.g., ACM, etc.)
- community characteristics
- clinical characteristics (e.g., CCI)

## 1.4.Exploratory Analyses

The exploratory analysis aims are to evaluate the effect of participation in the MVP program features on

- 6-month and 12-month primary care visits scheduled and attended / no show to a scheduled appointment
- 6-month and 12-month Healthy Days at Home
- 6-month and 12-month paid amount for the Medicare patient subgroup

## 2. BACKGROUND

A large portion of US health care costs is attributed to a small group of high-need, high-cost (HNHC) patients. The Agency for Healthcare Research and Quality recently examined nationwide Medical Expenditure Panel Survey data from 2014 and reported that 1% of US civilian population was accountable for more than 20% of health care spending, and 5% of the population for 50% (Dzau, et al. 2017, Mitchell, 2016). Similar patterns are seen at the health system level; Johnson et al. (2015) found that 3% of patients in an integrated safety-net health system accounted for 30% of charges.

To address HNHC patients' costs and high medical care utilization, health systems have been implementing a variety of care management programs as part of population health initiatives. The rise of these programs has been prevalent especially for Accountable Care Organizations (ACOs) and other value-based payment contracts (Peck et al., 2018). In general, these programs are characterized by establishing teams of clinicians and social workers who coordinate patients' medical care and address social determinants of health through referrals to community resources. The programs vary widely in theoretical foundations for interventions and individual features, which are a mix of medical and social services, and can have either episodic or longitudinal focus (Anderson, et al., 2015, Bodenheimer, 2013). There is not a consensus definition of the HNHC patient, thus selection criteria for these programs vary. One approach is based on clinical and functional characteristics of the patient, and the other approach identifies eligible patients as "super-utilizers" who accumulated a high number of ED visits and hospital admissions, with some programs using a combination of the two approaches (AHRQ, 2019, Johnson et al., 2015, Mann, et al., 2013).

Evaluations of care management programs for HNHC patients have been conducted using pre-post analysis and randomized controlled trials, both have shown mixed results (Baker, et al., 2018, Naylor et al, 2011). Recently, Powers, et al. (2020) conducted a randomized trial to evaluate CareMore Health's complex care management program on utilization of HNHC Medicaid patients between March 2017 and February 2018. Patients were screened based on a set of clinical and past healthcare use characteristics and randomized to receive the chronic care management program or usual care. Those randomized into the program were contacted by phone, and those who chose to enroll completed a comprehensive assessment and received a tailored care plan. The complex chronic program team consisted of a community health worker, social worker and a primary care physician (PCP). The authors found that patients randomized to receive complex care management had fewer total inpatient bed days (59% decrease) and fewer inpatient admissions (44% decrease) over a 12-month period. Healthcare costs were also lower in the group who received care management, mostly driven by the decrease in inpatient utilization. On the other hand, in the recent randomized controlled trial conducted to evaluate the Camden Coalition of Healthcare Providers hotspotting

program, Finkelstein, et al. (2020) found no effect of a promising care management program on HNHC patients' readmission rates 180 days after discharge. Nor did the authors find an effect on any other hypothesized outcomes. Similar to CareMore, patient eligibility was based on a complex set of clinical and past utilization characteristics. In the evaluation of Camden's program, patients were enrolled on a rolling base while in the hospital, and upon return home they received help from a multidisciplinary team of clinicians, social and community workers.

Several published studies used the pre-post approach (Lynch, et al., 2016). Pre-post analysis can, however, misleadingly suggest huge benefits of the program, while the decrease in utilization is simply an observation of regression to the mean; in other words, utilization would drop with or without the program. Johnson, et al. (2015) confirms this phenomenon. The authors found that at the individual level, person's high utilizer status changed over time, with less than 50% of super-utilizers remaining in the high utilization category seven months after being identified as high utilizers, and only 28% a year later. Finkelstein, et al. (2020) addressed the importance of conducting a randomized trial evaluation instead of a pre-post analysis. While a pre-post analysis using the same data as the RCT showed a 38 % decrease in readmissions for the intervention group, the RCT results implied that this decrease could not be attributed to the Camden hotspotting program.

Another approach applied in care management program evaluations is a pre-post design with a comparable control group created in absence of an RCT (Thompson, et al., 2018, Sevak, et al., 2018). Thompson, et al. (2018) evaluated a community navigator program where eligibility was determined based on having 11+ encounters (ED, IP and OBS) during a 12-month period and primary residence at a specific zip code. The cohort received help from community navigators for one year. The authors created a control group that met the 11+ encounters criteria for super-utilizers but had residence in different zip codes. The authors found that that patients participating in the program had a 13% larger reduction in hospital encounters and 8% reduction in hospital days than the control group.

The components of the MVP program at AH were adopted from the approach promoted by A. Boutwell, MD, Collaborative Healthcare Strategies (2018). Multi-visit utilization in the past is considered a manifestation of co-occurring medical, behavioral, and social needs, likely unmet or not adequately addressed. Care managers are trained to identify underlying causes for high utilization through listening and asking patient questions beyond clinical diagnoses and looking for patterns in care seeking (e.g., problems with logistics, sense of urgency, uncertainty, or convenience). The MVP program aims to engage the patient, develop trusting relationships, offer recommendations tailored to patient while avoiding "over-medicalization," and over time help the patient achieve stability. An example of the program implementation is the MAX series for Medicaid patients with high past utilization in New York State. Both inpatient and ED utilization for participants in the MAX series decreased after the program introduction; the evaluation method, however, was pre-post analysis (New York State Department of Health, 2017).

Evidence of effectiveness of care management programs varies because of differences in program features, outcomes studied, the underlying studied population eligibility and characteristics (e.g., all patients, Medicaid, patients with heart failures), and statistical methods employed for evaluation (from pre-post to randomized trials). Randomized trials such as this are needed to make causal inferences on a care management programs effectiveness, ability to identify subgroups of patients who benefit most from the programs, and to identify impactful program features.

### 3. RATIONALE

The AH MVP program was established by the Population Health's Care Management group to address the complex needs of patients with the highest volume of inpatient hospital visits at AH. Care management initiated its work with the first cohort of 600 MVP patients in January 2019. An additional 46 patients were added in August 2019. Pre-post descriptive results showed that the 2019 MVP cohort's inpatient hospital rate was lower in 2019 than in 2018. While this is a promising outcome, without a randomized controlled trial (RCT) causal inferences cannot be made about the effect of the MVP program. Regression to the mean is a competing potential reason for observing the rate decrease, with high utilizers having lower hospital use over time even in the absence of any interventions. Thus, the Population Health leadership seeks to conduct a definitive trial to rigorously evaluate the MVP program effectiveness.

The randomized trial will allow us to make causal inferences regarding the effect of the MVP program on hospital utilization and isolate this effect from the regression to the mean phenomenon. It will also address identification of patients who most benefit from the program by sociodemographic characteristics, economic indicators of communities where they live, and clinical characteristics. The insights gained from the RCT will (1) inform strategic decisions on how AH effectively deploys limited care management resources to its patients; (2) provide generalizable knowledge using a rigorous RCT framework to improve care management programs beyond AH; and (3) generate robust real-world data as input to develop a novel machine learning model to advance high risk patient segmentation.

This research project is a parallel group, randomized trial of a care management program which seeks to evaluate inpatient hospitalization and utilization of other acute care services during a 12-month period. The evaluation of this intervention has been designed to integrate into routine care and minimize frontline staff burden by deploying a pragmatic evaluation in a real-world setting.

### 4. SUBJECT SELECTION

#### 4.1. Subjects Accrual and Randomization

1. The list of patients meeting the inclusion criteria will be pulled from AH electronic data warehouse (EDW).
2. Based on chart review, patients not eligible for the MVP program due to exclusion criteria will be removed from the list. Programmatic subgroups will be identified among eligible patients
  - (1) Ambulatory Care Management (ACM) and Advanced Illness Program (AIM)
  - (2) Community Care Partners (CCP) and Community Care of NC (CCNC)
  - (3) Community Care Bridge (CCB)
3. Patients remaining on the list will be randomized 1:1 to Usual Care or MVP referral using stratification to maintain balance across defined programmatic subgroups.
4. The Care Management team will monitor and reach out to patients identified for enrollment in the MVP program during the study period. Patients assigned to usual care will not be enrolled into the MVP program.

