## 5. OVERALL DESIGN

### 5.1. Variables

#### 5.1.1. Primary Outcome Variable

The primary outcome variable is the number of inpatient (IP) hospital encounters over a 12-month period.

- IP encounter is defined as an admission to an AH acute care hospital.

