### **5.4. Patient Graduation from the MVP program**

Participation in the MVP program ends if the care manager stops monitoring the patient's health and stops reaching out to the patient. Reasons include:

- a) Patient died
- b) Patient relocated
- c) Patient was incarcerated

The below reasons do not result in ending the MVP participation. Instead, the MVP care manager continues to quietly monitor the patient's health and coordinate services if needed but does not reach out directly to the patient.

- a) Patient no longer wishes to participate
- b) Patient enrolled in palliative/hospice care while enrolled in the MVP program
- d) Patient moved to nursing home or assisted living while enrolled in the MVP program

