### 6.1. Power Analysis

The outcome of interest is the number of IP hospital encounters over a 6-month period. The research (alternative) hypothesis is that the enrollment in the MVP program will lead to a larger decrease in IP encounters compared to usual care; the null hypothesis is no change in the percentage decrease across both arms of the study.

In order to determine the outcome variable value for the power analysis we used historical data of IP hospital encounters for patients enrolled in the MVP program in 2019 whom we expect to be similar to MVP enrollees in this study. To determine the sample size we considered the Care Management's requested size of 600 enrollees in the MVP program cohort. We estimated that the MVP program will serve 146 existing enrollees, who are not eligible for the study, and 454 new enrollees, who are eligible for the study. We used the following inputs for the power analysis: the average number of IP encounters was 6.5 in 2018, and it decreased 54% in 2019. We assumed that there are equal variances in both the treatment group and the control group and performed the calculations with a standard deviation of 0.45. We assumed there are 910 patients in the study population, with 454 patients randomized in the treatment group (MVP program) and 454 patients randomized in the control group (usual care). We assumed that the attrition rate due to death and relocation is 35%, resulting in 295 patients per group.

The sample size of 295 (in each group) achieves 80% power to reject the null hypothesis of equal percentage decreases in both groups when the mean difference is 10.4% points with a standard deviation of 0.45. In other words, with our sample size we would have the statistical power to detect a 10.4% point

reduction in IP hospital encounters for the MVP group compared to the control group. The 10.4% point difference (between the 54% drop for the MVP group compared to 43.6% drop for the control group) translates into a 21.3% relative reduction in the number of IP hospital encounters thanks to the MVP program. The level of significance is 0.05; a two-sided two sample t test was used (assuming the outcome follows a normal distribution). The sample size calculation was performed using the PASS software (2020).

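### No entry criterion requires patients to be alive, in the area and not incarcerated at randomization, so some who cannot respond to the program may be randomized, which dilutes the absolute effect

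*Combined protocol and SAP*

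**What the plan says.** Section 4.2.1 admits adults with four or more inpatient visits in 2019. Section 4.1 describes one removal step before 1:1 randomization: after chart review, "patients not eligible for the MVP program due to exclusion criteria will be removed from the list". The exclusions in section 4.2.2 are prior MVP enrollment, oncology navigation, hospice or palliative care, an outside primary care provider, and skilled nursing residence. Neither list mentions vital status, relocation or incarceration.

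Section 5.2 starts the intervention group at one time point chosen by care management leadership and gives no calendar date. Section 6.3 accrues data for 365 days from enrollment.

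Section 5.4 states: "Participation in the MVP program ends if the care manager stops monitoring the patient's health and stops reaching out to the patient". The reasons it gives are death, relocation and incarceration.

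Sections 4.3 and 6.2 analyze everyone who meets the criteria by intention to treat. On the primary outcome, section 5.1.1 says: "IP encounter is defined as an admission to an AH acute care hospital". Section 6.2 reports count outcomes as marginal effects, and its model shows no term for time at risk.

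Two other passages treat these patients differently. Section 6.1 takes them out of the sample: "We assumed that the attrition rate due to death and relocation is 35%, resulting in 295 patients per group". Section 5.1.4 sets the treatment indicator to 1 only for a patient who was assigned to MVP and is flagged active in PatientPing, and to 0 otherwise.

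**The concern.** There is an interval of unstated length between the 2019 stays and the common start date. The population is one in which the protocol itself plans for substantial death and relocation. A patient who has died, moved away or been incarcerated in that interval still meets every written criterion.

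Such a patient cannot respond to care management. Someone already dead has no possible admission in either arm. Someone who has relocated or is incarcerated would probably have few admissions to Atrium Health (AH) hospitals, the only ones that count. Including them shrinks the absolute difference between arms and takes up MVP places, which section 5.2 says are limited by capacity.

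The coding in section 5.1.4 is a further risk. An MVP-assigned patient found to be dead or gone may never be flagged active. Read literally, the indicator would then place that patient in the comparison group and lower its mean.

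**Working it through.** **Inputs from section 6.1.** "The level of significance is 0.05; a two-sided two sample t test was used". "The sample size of 295 (in each group) achieves 80% power to reject the null hypothesis" of equal decreases "when the mean difference is 10.4% points with a standard deviation of 0.45". The difference is "between the 54% drop for the MVP group compared to 43.6% drop for the control group". There are 454 randomized per arm.

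**Input not in the documents.** The share f of each arm that is dead, relocated or incarcerated before the start date. I assume 5%, 10% and 20%, equal in both arms in expectation because of randomization.

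**Step 1: reproduce the plan's figure.** Normal approximation: power = Φ(d / (SD·√(2/n)) − 1.96).
- 454 × 0.65 = 295.1, which matches 295 per group.
- With n = 295, the standard error is 0.45 × √(2/295) = 0.0371. Then 0.104/0.0371 = 2.81, and Φ(2.81 − 1.96) gives 0.801. The exact t test gives 0.800. The stated 80% reproduces.
- With all 454 per arm, the standard error is 0.0299 and power is 0.936.

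**Step 2: keep the affected patients.** Suppose they have no admissions in either arm. They then contribute no difference, and d becomes (1 − f) × 10.4 points with n = 454. For example, at f = 10%: 0.0936/0.0299 = 3.13, and Φ(3.13 − 1.96) = 0.88.

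**Step 3: remove them without replacement.** The difference stays at 10.4 points and n becomes 454 × (1 − f).

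| Assumed f | Difference if kept (points) | Power if kept (n = 454) | n per arm if removed | Power if removed |
|---|---|---|---|---|
| 5% | 9.9 | 0.911 | 431 | 0.924 |
| 10% | 9.4 | 0.880 | 409 | 0.910 |
| 20% | 8.3 | 0.796 | 363 | 0.876 |

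These figures hold the SD at 0.45 and assume no other loss. Letting the SD reflect the mixture changes power if kept only to 0.908, 0.875 and 0.793.

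**Step 4: the coding in section 5.1.4.** Suppose there is no true effect, affected patients have no admissions, and every affected MVP-assigned patient is never activated.
- The group coded 1 has mean μ.
- The group coded 0 has 454 + 454f patients, with total admissions 454(1 − f)μ.
- The ratio of means, coded 1 to coded 0, is (1 + f)/(1 − f): 1.05/0.95 = 1.11, 1.10/0.90 = 1.22, and 1.20/0.80 = 1.50.

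With no true effect, MVP would appear to raise admissions.

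**The case against.** **Chart review may already catch many of these patients.** Section 5.2 has leadership review each chart and assign a care group by insurance and care needs, partly by county. A recorded death, and often a move, could surface there. The outside-provider exclusion would catch some relocations. This stands as a reason to expect a smaller f. But the protocol gives reviewers no criterion on which to remove such a patient.

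**The effect is small if patients are analyzed as assigned.** This also stands. Power stays near 80% even at f = 20%, and a ratio of means would be little affected because (1 − f) enters both arms. The absolute marginal effect, which section 6.2 reports, does shrink.

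Several stronger readings are tempting, and the documents do not support them:
- *All such patients are scored as zero admissions.* No passage says so. It follows for those already dead, but relocated or incarcerated patients may still be admitted to an AH hospital. For the same reason, not everyone removed would be without information.
- *The 35% gives the number affected.* It is planned loss from the randomized sample, with no period stated. The start date is not given either, and the 2020 access dates in the reference list are not trial dates. No count of affected patients can be derived.
- *Deaths before the start enter the mortality outcome.* The 365-day window in section 6.3 largely rules this out.
- *Power falls below 80% because such patients sit among the 295.* Section 6.1 reaches 295 after already taking out death and relocation.
- *The entry criteria are the wrong way round, because hospice and nursing-home patients are excluded although the program keeps them.* Section 5.4 governs exit after enrollment, and for those patients direct outreach stops. Excluding them at entry is coherent.

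**Conclusion.** The concern holds as a gap in the entry criteria with a modest, conditional cost. As written, patients who are dead, relocated or incarcerated before the start date can be randomized and belong to the intention-to-treat population.

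If they are analyzed as assigned, the result is dilution without bias. At an assumed 10%, the detectable contrast falls from 10.4 to 9.4 points, and removing them would raise power from about 0.88 to 0.91 despite the smaller sample. These figures rest on the assumed f, on no admissions among those affected, and on 454 per arm with no other loss.

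Bias arises only if the active flag in section 5.1.4 is applied literally and affected MVP patients are never activated. It would run against the program. That coding also conflicts with section 6.2, which defines the parameter of interest as the effect of being randomized.

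**What to change.** 1. Add an exclusion to section 4.2.2 for patients recorded in the data warehouse or chart as having died by a single fixed cut-off date immediately before randomization. Apply it to the whole list before allocation, so that both arms are treated alike.
2. At the same date, also remove patients recorded as having relocated outside the service area or as incarcerated, where such data exist.
3. In section 5.1.4, define Treatment by random assignment only, and record the active flag as a separate variable.
4. Reconcile section 6.1, which takes deaths and relocations out of the sample, with sections 4.3 and 6.2, which keep everyone.

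The cost is one query of vital status and address before randomization and a few lines of text. The downside is a slightly shorter list and the loss of a few movers who might still have used AH hospitals. Relocations and incarcerations that are not recorded will still be missed, but equally in both arms in expectation.
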